5.1.4 Immunization Compliance

Immunization compliance will be recorded at the time of study immunization on day 1 at visit 2. Study immunization will take place in the clinical unit. The exact day and time of study vaccine administration will be documented.

Observation Period: Subjects will remain under observation for 1 hour postimmunization, (provided no reactions have occurred). If a subject experiences significant clinical symptoms, in the opinion of the investigator, then additional direct supervision may be required as needed for management of the symptoms.

5.1.5 Criteria for Continuation of Immunization

Formal Stopping Rules for Individual Subjects:

Individual subjects will be discontinued from the study if:

- Subject is lost-to-follow-up despite reasonable efforts by the investigator to locate the subject.
- Subject voluntarily withdraws from the study at any time for any reason.

Formal Stopping Rules for Cohorts:

No additional subjects will be randomized or dosed in the study until the events below occurring in a subject who received ASP3772 are reviewed by the DEC and it is acceptable to resume cohort immunization.

- Unexplained death of a subject.
- Serious acute hypersensitivity reaction in a subject.
- One of the sentinel subjects experiences an AE of severe intensity related to ASP3772, when sentinel subjects are required.
- An SAE of the same character occurs in at least 2 subjects or 1 subject experiences a vaccine-related SAE.
- Grade 3 or higher lab abnormality considered related to the immunization occurs in 2 or more subjects [FDA Guidance for Industry, 2007].
- The same type of reactogenicity event assessed as Grade 3 or higher occurs in 2 or more subjects, or 1 of the sentinel subjects experiences a reactogenicity event assessed as Grade 3 or higher, using the FDA toxicity grading scale for preventative vaccines [FDA Guidance for Industry, 2007].
- An imbalance of unsolicited AEs between ASP3772 and PCV13 is observed.

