Adults 18 to 64 years of age - PCV13 Naïve Subjects (Group 1):

Subjects will receive 1 immunization of ASP3772 or PCV13 administered on day 1. Follow-up study visits will be conducted at 7, 30 and 180 days postimmunization. The final study visit at day 180 may be conducted via telephone call.

Stage 2:

Elderly 65 to 85 years of age - PCV13 Naïve Subjects (Group 2):

Subjects will receive 1 immunization of ASP3772 or PCV13 administered on day 1.

Follow-up study visits will be conducted at 7, 30 and 180 days postimmunization. The final study visit at day 180 may be conducted via telephone call.

Elderly 65 to 85 years of age - Previous PCV13 Exposed Subjects (Group 3):

A third group of nonrandomized subjects previously vaccinated with PCV13 will be enrolled and receive a booster immunization with PPSV23 only on day 1. A follow-up visit will be conducted at 30 days postimmunization and this visit will also serve as the final study visit.

Formal Stopping Rules:

Early Termination of Subjects:

Individual subjects will be discontinued from the study if:

- Subject is lost-to-follow-up despite reasonable efforts by the investigator to locate the subject.
- Subject voluntarily withdraws from the study at any time for any reason.

Formal Stopping Rules for Cohorts:

No additional subjects will be randomized or dosed in the study until the events below occurring in a subject who received ASP3772 are reviewed by the DEC and the DEC recommends that it is acceptable to resume cohort immunization.

- Unexplained death of a subject.
- Acute hypersensitivity reaction in a subject.
- One of the sentinel subjects experiences an AE of severe intensity related to ASP3772, when sentinel subjects are required.
- An SAE of the same character occurs in at least 2 subjects or 1 subject experiences a vaccine-related SAE.

02 Dec 2019 Astellas Page 21 of 111

- Grade 3 or higher lab abnormality considered related to the immunization occurs in 2 or more subjects [FDA Guidance for Industry, 2007].
- The same type of reactogenicity event assessed as grade 3 or higher occurs in 2 or more subjects, or 1 of the sentinel subjects experiences a reactogenicity event assessed as grade 3 or higher, using the FDA toxicity grading scale for preventative vaccines [FDA Guidance for Industry, 2007].
- An imbalance of unsolicited AEs between ASP3772 and PCV13 is observed.

Decision Process for Dose Escalation:

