After both sentinel subjects in a cohort have completed study procedures on day 7, the decision to open enrollment for the full cohort will be determined by DEC based on review of the Day 7 reactogenicity and safety data of those 2 sentinel subjects.

After all vaccinated subjects in a cohort have completed study procedures on day 7, the decision to dose escalate to next cohort within both stages will be determined by DEC based on the review of the following:

- Day 7 reactogenicity and safety data (AEs, ECG, clinical laboratory tests, vital signs) from the current cohort.
- Day 7 reactogenicity and safety data from all subjects of the preceding cohort(s).

To evaluate safety by DEC, day 7 data is needed from a minimum of 38 subjects in each cohort for Stage 1.

Stage 2 will commence based on DEC review of the following:

- Day 7 reactogenicity and safety data (AEs, ECG, clinical laboratory tests, vital signs) from all subjects in Stage 1.
- Day 30 safety data (AEs, ECG, clinical laboratory tests, vital signs) from all subjects in Stage 1.

To evaluate safety by DEC, day 7 data is needed from a minimum of 129 subjects in each cohort for Stage 2. Further details around the dose escalation process are included in the DEC charter.

Dose Escalation Criteria:

Depending on the nature, frequency and severity of the safety profile observed in the study, and the study vaccine received, the DEC will decide whether to:

- Proceed with dose escalation.
- Proceed from Stage 1 to Stage 2.
- Determine need of sentinel dosing in Stage 2 cohorts.
- Stop dose escalation.

Dose escalation may proceed unless 1 (or more) of the following apply in subject(s) receiving ASP3772:

- Two or more subjects experience an AE of severe intensity related to ASP3772 or 2 or more subject(s) experience a reactogenicity event of grade 3 or higher intensity related to ASP3772.
- One or more subject(s) experience a SAE related to ASP3772.

02 Dec 2019 Astellas Page 22 of 111

Endpoints for Evaluation:

Stage 1:

Primary Endpoints

Safety and tolerability of ASP3772 will be assessed by:

- Treatment-emergent adverse events (TEAEs) including MAAEs, PIMMCs, NOCDs
- Vital signs (body temperature, blood pressure and pulse rate)

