5.1.2 Increase or Reduction in Dose of the Study Vaccine(s)

Decision Process for Dose Escalation:

After both sentinel subjects in a cohort have completed study procedures on day 7, the decision to open enrollment for the full cohort will be determined by DEC based on review of the Day 7 reactogenicity and safety data of those 2 sentinel subjects.

After all vaccinated subjects in a cohort have completed study procedures on day 7, the decision to dose escalate to next cohort within both stages will be determined by DEC based on the review of the following:

- Day 7 reactogenicity and safety data (AEs, ECG, clinical laboratory tests and vital signs) from the current cohort.
- Day 7 reactogenicity and safety data from all subjects of the preceding cohort(s).

To evaluate safety by DEC, day 7 data is needed from a minimum of 38 subjects in each cohort for Stage 1.

Stage 2 will commence based on DEC review of the following:

- Day 7 reactogenicity and safety data (AEs, ECG, clinical laboratory tests and vital signs) from all subjects in Stage 1.
- Day 30 safety data (AEs, ECG, clinical laboratory tests and vital signs) from all subjects in Stage 1.

To evaluate safety by DEC, day 7 data is needed from a minimum of 129 subjects in each cohort for Stage 2. Further details around the dose escalation process are located in the DEC charter.

02 Dec 2019 Astellas Page 53 of 111

Dose Escalation Criteria:

Depending on the nature, frequency and severity of the safety profile observed in the study, and the study vaccine received, the DEC will decide whether to:

- Proceed with dose escalation.
- Proceed from Stage 1 to Stage 2.
- Determine need of sentinel dosing in Stage 2 cohorts.
- Stop dose escalation.

Dose escalation may proceed unless 1 (or more) of the following apply in subject(s) receiving ASP3772:

- Two or more subjects experience an AE of severe intensity related to ASP3772 or 2 or more subject(s) experience a reactogenicity event of grade 3 or higher intensity.
- One or more subject(s) experience a SAE related to ASP3772.

Stopping criteria for study immunization are described in detail in [Section 5.1.5 Criteria for Continuation of Immunization].

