5.5.2 Definition of Serious Adverse Events (SAEs)

An AE is considered "serious" if, in the view of either the investigator or sponsor, it results in any of the following outcomes:

- Results in death
- Is life-threatening (an AE is considered "life-threatening" if, in the view of either the investigator or sponsor, its occurrence places the subject at immediate risk of death. It does not include an AE that, had it occurred in a more severe form, might have caused death)
- Results in persistent or significant disability/incapacity or substantial disruption of the ability to conduct normal life functions
- Results in congenital anomaly, or birth defect
- Requires inpatient hospitalization (except for planned procedures as allowed per study)
 or leads to prolongation of hospitalization (except if prolongation of planned
 hospitalization is not caused by an AE). Hospitalization for
 treatment/observation/examination caused by AE is to be considered as serious.)
- Other medically important events (defined in paragraph below)

02 Dec 2019 Astellas Page 60 of 111

Medical and scientific judgment should be exercised in deciding whether expedited reporting is appropriate in other situations, such as important medical events that may not be immediately life-threatening or result in death or hospitalization but may jeopardize the subject or may require intervention to prevent 1 of the other outcomes listed in the definition above. These events, including those that may result in disability/incapacity, usually are considered serious. Examples of such events are intensive treatment in an emergency room or at home for allergic bronchospasm; blood dyscrasias or convulsions that do not result in hospitalization; or development of drug dependency or drug abuse.

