12.10 Common Serious Adverse Events

For this phase 1/2 clinical study, there is no list of common SAEs for which a single occurrence will be excluded from IND safety reporting.

02 Dec 2019 Astellas Page 96 of 111

INFORMATION DISCLOSURE TO THE SUBJECTS

02 Dec 2019 Astellas Page 98 of 111

13 ATTACHMENT 1: NONSUBSTANTIAL AMENDMENT 2

I. The purpose of this amendment is:

Non-Substantial Changes

1. Minor Administrative-type Changes

DESCRIPTION OF CHANGE:

Include minor administrative-type changes, e.g., typos, format, numbering, consistency throughout the protocol.

RATIONALE:

To provide clarifications to the protocol and to ensure complete understanding of study procedures.

2. Update Planned Study Period

DESCRIPTION OF CHANGE:

The planned study period for this Stage 2 of this trial is moved out a quarter.

RATIONALE:

This revision is made due to reflect the current study timelines.

3. Increase in Number of Study Sites

DESCRIPTION OF CHANGE:

The number of study sites for both Stage 1 and Stage 2 is increased.

RATIONALE:

The site numbers are increased to support subject recruitment in Stage 2 Group 2.

4. Modification to Exclusion Criterion #11

DESCRIPTION OF CHANGE:

Exclusion criterion #11 is revised to remove the requirement to exclude subjects who are positive for hepatitis B core antibody (HBc) during serology testing.

RATIONALE:

It was determined that hepatitis B surface antigen (HBsAg) is sufficient to confirm evidence of chronic hepatitis B virus infection.

5. Extension of Screening Period

DESCRIPTION OF CHANGE:

The screening period for Stage 2, Groups 2 and 3, is extended to 40 days before dosing.

02 Dec 2019 Astellas Page 99 of 111

RATIONALE:

The screening period is extended for Groups 2 and 3 to minimize the number of subjects who may require rescreening procedures due to the timing of cohort data reviews.

6. Modification to Stopping Rules

DESCRIPTION OF CHANGE:

The formal stopping rules for cohorts is updated such that enrollment/dosing will be stopped when 1 of the sentinel subjects experiences an ASP3772-related adverse event (AE) of severe intensity only when sentinel subjects are required.

RATIONALE:

Based on the dose escalation committee review of safety data in previous cohorts, it was decided that sentinel subjects will no longer be required for Cohort 5 onward.

II. Amendment Summary of Changes:

IIa. Non-substantial Changes

II. Contact Details of Key Sponsor's Personnel						
WAS:						

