5.1.5 Criteria for Continuation of Immunization

WAS:

Formal Stopping Rules for Cohorts:

No additional subjects will be randomized or dosed in the study until the events below occurring in a subject who received ASP3772 are reviewed by the DEC and it is acceptable to resume cohort immunization.

- Unexplained death of a subject.
- Acute hypersensitivity reaction in a subject.
- One of the sentinel subjects experiences an AE of severe intensity related to ASP3772.
- An SAE of the same character occurs in at least 2 subjects or 1 subject experiences a vaccine-related SAE.
- Grade 3 or higher lab abnormality considered related to the immunization occurs in 2 or more subjects [FDA Guidance for Industry, 2007].
- The same type of reactogenicity event assessed as Grade 3 or higher occurs in 2 or more subjects, or 1 of the sentinel subjects experiences a reactogenicity event assessed as Grade 3 or higher, using the FDA toxicity grading scale for preventative vaccines [FDA Guidance for Industry, 2007].
- An imbalance of unsolicited AEs between ASP3772 and PCV13 is observed.

IS AMENDED TO:

Formal Stopping Rules for Cohorts:

No additional subjects will be randomized or dosed in the study until the events below occurring in a subject who received ASP3772 are reviewed by the DEC and it is acceptable to resume cohort immunization.

- Unexplained death of a subject.
- Acute Serious acute hypersensitivity reaction in a subject.
- One of the sentinel subjects experiences an AE of severe intensity related to ASP3772, when sentinel subjects are required.
- An SAE of the same character occurs in at least 2 subjects or 1 subject experiences a vaccine-related SAE.
- Grade 3 or higher lab abnormality considered related to the immunization occurs in 2 or more subjects [FDA Guidance for Industry, 2007].
- The same type of reactogenicity event assessed as Grade 3 or higher occurs in 2 or more subjects, or 1 of the sentinel subjects experiences a reactogenicity event assessed as Grade 3 or higher, using the FDA toxicity grading scale for preventative vaccines [FDA Guidance for Industry, 2007].
- An imbalance of unsolicited AEs between ASP3772 and PCV13 is observed.

5 Immunizations and Evaluation

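### The synopsis and the body of Protocol Version 2.1 word two safety decision rules differently: the hypersensitivity pause and the Grade 3 reactogenicity block on dose escalation

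*Protocol*

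**What the plan says.** **Rule 1, cohort pause after hypersensitivity.** The synopsis and Protocol 5.1.5 each list formal stopping rules for cohorts. Both halt randomization and dosing, pending DEC review, after listed events in an ASP3772 recipient.

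- Synopsis: "Acute hypersensitivity reaction in a subject".
- Section 5.1.5: "Serious acute hypersensitivity reaction in a subject".

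The change log in Attachment 1 marks the edit to 5.1.5 as "Acute Serious acute hypersensitivity reaction in a subject" (deleted and inserted words run together). The rationale given there for modifying the stopping rules concerns sentinels only: after DEC review of earlier cohorts, "it was decided that sentinel subjects will no longer be required for Cohort 5 onward". The synopsis carries that sentinel edit ("One of the sentinel subjects experiences an AE of severe intensity related to ASP3772, when sentinel subjects are required") but not the added word *serious*.

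**Rule 2, block on dose escalation.** The synopsis and Protocol 5.1.2 share a lead-in that limits the criteria to ASP3772 recipients. They then differ.

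- Synopsis: "2 or more subject(s) experience a reactogenicity event of grade 3 or higher intensity related to ASP3772".
- Section 5.1.2: "2 or more subject(s) experience a reactogenicity event of grade 3 or higher intensity", where the clause ends.

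Protocol 4.4.1 says that when events meet criteria that could stop escalation, assignment is revealed for those subjects to establish whether the events are related to ASP3772. SAP 7.5.2 lets the investigator judge a solicited reaction not related, for the purpose of a second summary table.

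**The concern.** Safety and tolerability are the primary objective of both stages, and these rules govern when dosing pauses and when the dose rises. For some events the two texts call for different actions. After one non-serious acute hypersensitivity reaction in an ASP3772 recipient, the synopsis stops all dosing pending review, while the corresponding bullet of 5.1.5 does not. After two Grade 3 reactions in ASP3772 recipients, at least one of them judged unrelated, 5.1.2 blocks escalation while the same clause of the synopsis does not.

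The differences run in opposite directions. A convention that the body prevails, or that the synopsis prevails, would therefore adopt the looser wording of one rule.

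**Working it through.** **Side-by-side comparison (current text only)**

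| Event in ASP3772 recipients | Synopsis | Body | Stricter text |
|---|---|---|---|
| One serious acute hypersensitivity reaction | pause | pause (5.1.5) | same |
| One non-serious acute hypersensitivity reaction, no other trigger met | pause | no pause (5.1.5) | synopsis |
| Two subjects with Grade 3 or higher reactogenicity, both related | block | block (5.1.2) | same |
| Two subjects with Grade 3 or higher reactogenicity, fewer than two related | no block from this clause | block (5.1.2) | body |

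**How wide is the rule 1 gap?** Protocol 5.5.2 counts important medical events as serious even without hospital admission, and gives as an example "intensive treatment in an emergency room or at home for allergic bronchospasm". Many acute allergic reactions of concern would therefore already be serious. What remains is the non-serious reaction that meets no other pause trigger. The documents give no rate for these, so no figure can be attached.

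**How wide is the rule 2 gap?** It exists only if a Grade 3 reaction in an ASP3772 recipient can be judged unrelated for the escalation decision. Let p be the any-cause rate of Grade 3 or higher reactogenicity per ASP3772 recipient, r the share judged related, and n = 99 the ASP3772 recipients in a Stage 2 cohort (Protocol 2.2.1). Assume subjects are independent and events are counted within one cohort.

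- Block under 5.1.2: P(X ≥ 2) = 1 − (1 − p)^99 − 99p(1 − p)^98.
- Block under the synopsis: the same formula with p replaced by p × r.

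Worked case, p = 0.02: (0.98)^99 = 0.135 and 99 × 0.02 × (0.98)^98 = 0.273, so P = 1 − 0.135 − 0.273 ≈ 0.59.

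Both p and r are assumptions; the documents give neither. The r = 100% column is also the 5.1.2 result.

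| Assumed p | r = 100% | 95% | 90% | 75% | 50% |
|---|---|---|---|---|---|
| 1% | 0.261 | 0.242 | 0.224 | 0.170 | 0.088 |
| 2% | 0.591 | 0.563 | 0.534 | 0.438 | 0.261 |
| 3% | 0.801 | 0.777 | 0.751 | 0.655 | 0.438 |
| 5% | 0.961 | 0.952 | 0.941 | 0.890 | 0.711 |

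From unrounded values, the gap between the two texts is zero at r = 100%, 1 to 3 percentage points at 95%, 2 to 6 at 90%, 7 to 15 at 75% and 17 to 36 at 50%. The table shows that the answer depends almost wholly on r. It does not estimate the effect in this trial.

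**Which decisions remain?** Version 2.1 records that sentinels were dropped from Cohort 5 onward after review of earlier cohorts, and Cohort 6 is the top dose. Rule 2 can therefore matter for at most two escalations (Cohort 4 to 5, and 5 to 6), perhaps only the last. Rule 1 applies to dosing in whatever remains of Stage 2.

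**The case against.** The strongest reply is that rule 2 may contain no operational conflict. Section 4.4.1 settles relatedness by revealing which vaccine was given. If that is all that *related* means, the phrase in the synopsis adds little to a lead-in already limited to ASP3772 recipients, and both texts give the same decision. That is a reasonable reading, but 4.4.1 does not exclude a further causality judgement, so the wording stays open.

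Other safeguards also overlap under both texts. Same-type Grade 3 or higher reactions in two or more subjects pause dosing whatever their cause, as does one vaccine-related SAE or an imbalance of unsolicited AEs. Two severe AEs related to ASP3772 block escalation. The DEC may request any assignment and may stop escalation on the overall safety profile. This stands and is why the gap is narrow. The DEC charter may settle either rule, but it is not among the documents.

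Three stronger readings are tempting and are not supported.

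- *Section 5.1.2 has simply lost a phrase that should be put back.* Section 4.4.1 leans that way, but the reactogenicity pause rule has no relatedness condition in either text, so an any-cause count also fits the protocol. Adding the phrase would loosen a safety rule in a first-in-human trial on inference alone.
- *The conflict moves the chance of a block by tens of percentage points.* At the assumed rates, gaps above about 15 points appear only in the column with half of the reactions judged unrelated. SAP 7.5.2 shows that such a judgement is possible for a summary table, not how often it occurs or that it governs escalation.
- *The hypersensitivity rule was loosened without justification.* The log shows a deliberate edit to 5.1.5, and a synopsis bullet left behind is the likeliest explanation. Not all of the change log is available here, so a logged synopsis change or a further reason cannot be ruled out.

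**Conclusion.** The conflict is real on both rules, because it lies in the current Version 2.1 text and does not depend on the amendment log. It is minor. It bears only on non-serious acute hypersensitivity that meets no other trigger and on Grade 3 reactions judged unrelated, in what remains of Stage 2. The action at stake is a pause or a block under DEC review, not termination. No alpha, power or endpoint is affected.

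Confidence is high on the wording and low on the consequence. Rule 1 has no usable rate. Any figure for rule 2 rests on an assumed event rate, an assumed share judged related, and the assumption that relatedness means more than having received ASP3772. The documents do not show which wording of rule 2 was intended.

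**What to change.** The sponsor confirms the intended wording of both rules and makes the synopsis, 5.1.5, 5.1.2 and the DEC charter identical.

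- **Rule 1:** if the restriction was intended, add *serious* to the synopsis bullet and record the reason. If not, restore the unrestricted bullet in 5.1.5.
- **Rule 2:** either add the relatedness condition to 5.1.2 or delete it from the synopsis. If it is kept, state whether it means a causality judgement or only that the subject received ASP3772.
- **Until confirmed:** apply the stricter wording of each, that is, the synopsis for hypersensitivity and 5.1.2 for reactogenicity.

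The cost is a few words in a short amendment, one sponsor confirmation and a check of the charter. No analysis or sample size changes.
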